When a cohort large enough is available, randomization into STEP-Home or PCGT will occur and participation in the study begins (i.e., Time 1; T1: Pre), during which we will consent, administer the baseline assessments, randomly assign to either the STEP-Home or the PCGT arm, and schedule the treatment sessions. All participants will be assessed at the following 5 outcome points: Screening, at randomization (T1: Assessment), during treatment 4-week skills check (T2: Brief Skills Check), during treatment 8-week skills check (T3: Brief Skills Check), post-intervention (T4: Assessment), and at 3-months follow up (T5: Assessment). Assessments and skills checks are all self-report; therefore, blinded assessors are not required. Participants who decide to leave the program early will be asked to complete all assessments via secure Qualtrics link sent in MyHealtheVet or via postal mail service according to the RCT timeline following the intent-to-treat format, but will not be required to do so. Veterans will participate in their assigned treatment arm 1 day/week for approximately 2 hours. Replicating our SPiRE feasibility and preliminary effectiveness study [1], staff members will work in pairs when running groups. These same two staff members will offer to meet individually with Veterans before or after group approximately 4 to 6 times/workshop; it will be the Veterans' choice whether they participate in these individual meetings.

Assessments (T1, T4, and T5) may be done in person or online (see Data Security Section for description of Qualtrics online data entry). Brief Skills Checks (T2 & T3) may also be done in person or online.

**Randomization Figure.** T1 = Baseline Assessment; T2 = 4-week Skills check; T3 = 8-week Skills check; T4 = 12-week Post-Intervention Assessment; T5 = 24-week Follow-up Assessment.

- Assessments = T1, T4, and T5; Reimbursement = \$20
- Brief Skills Checks = T2 & T3; Reimbursement = \$0

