**(2) Comparison Group = PCGT.** A nonspecific comparison design [64] was selected to allow greater certainty that STEP-Home treatment effectiveness is due to specific aspects of the key ingredients of the experimental therapy (STEP-Home) and not merely to nonspecific therapeutic factors. PCGT was initially developed by Schnurr et al. [65] to include all elements of effective PTSD treatment that are not specifically trauma-focused. PCGT is a credible and clinically acceptable treatment often used as a control condition in PTSD trials with notably low drop out rates [65-67]. It is a nonspecific and supportive intervention to control for the nonspecific benefits of the group experience (e.g., therapist contact, instillation of hope, expectation of improvement). PCGT is fully manualized for group delivery and can be easily matched to STEP-Home as an active control arm (e.g., [65-67]). It will focus on identifying and discussing current life stressors that contribute to reintegration difficulties, psychoeducation, and promotion of wellness and physical health. Similar to the STEP-Home group, PCGT will contain homework assignments, involving monitoring diaries of stressful situations and when symptoms cause impairment in social and occupational functioning, and will also meet for ~1.5 - 2 hours a week for 12 weeks. Staff members will also offer to meet individually with Veterans enrolled in PCGT before or after group approximately 4 - 6 times over the 12 weeks. PCGT and individual sessions will not include the components that form the key ingredients or core skills of STEP-Home: CBT-based active PS, ER, or AT. Rather, PCGT employs Yalom's [68, 69] model of group therapy with a "here-and-now" focus and emphasizes the process of interpersonal learning, group cohesion, and group support. Although focus of group discussions will often be on group members' current problems, active CBT-based directive PS techniques used in STEP-Home will not be employed in the PCGT control condition. Content for group discussions will mimic STEP-Home topics including: Vocational, Community Reintegration, Psychoeducation & Destigmatization (gateway to VA care), Substance Misuse, Anger Management, Veteran-to-Veteran Support, and Family/Support System Involvement.

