Statistical Methods by Research Aims. The primary analysis for each aim will use an intent-to-treat (ITT) approach (i.e., all randomized subjects will be used in the analysis). ITT is optimal since it provides the least biased estimate of the treatment effect and the randomization balances STEP-Home and PCGT groups on known and unknown baseline confounders. This approach is appropriate for the proposed study given an anticipated low attrition rate of ~17% (based on attrition rates observed in our SPiRE study and Mt. Sinai's STEP RCT). We will implement quality assurance procedures to minimize protocol deviations and ensure correct treatment assignment according to the randomization. As a sensitivity analysis, we will conduct a per-protocol analysis in the subset of participants who complete an adequate amount of treatment ( $\geq 80\%$  of weekly sessions). We will assess the assumptions of homogeneity of variance and normality of residuals for each regression model and apply an appropriate transformation of the outcome if needed. We will address missing data, under the assumption of missing at random, using multiple imputation. Any subject characteristics associated with both the treatment group and primary outcome measure will be adjusted for in the final statistical model as specified in each aim.

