**Aim 1. Examine treatment effects of STEP-Home on primary outcomes relative to PCGT:**

***Hypothesis 1A. Participants randomized into the STEP-Home intervention will show improvement on reintegration, readjustment, and anger post-intervention (expressed by lower scores; less difficulty).***

Military to Civilian Questionnaire (M2CQ), Post-Deployment Readjustment Inventory (PDRI), and State-Trait Anger Expression Inventory (STAXI-2) scores post-intervention (T4)  $<$  baseline (T1)

Statistical Methods: Paired t-tests will evaluate the difference between pre- (T1) and post-scores (T4), with a separate analysis for each primary outcome.

***Hypothesis 1B. Participants randomized into STEP-Home will show greater improvement in primary outcomes as compared to PCGT.***

1B.1: Change scores baseline (T1) to post-intervention (T4) STEP-Home  $>$  PCGT

1B.2: Post-intervention (T4) primary outcome scores STEP-Home  $<$  PCGT

Statistical Methods: Mixed models (PROC MIXED in SAS) will evaluate pre-post differences, with a separate model for each primary outcome. The Satterwaite option will be used to account for the clustering of subjects within cohorts (identified in Section 6.2) and calculate degrees of freedom accounting for any missing data. Group (STEP-Home/PCGT) will be the between-subjects factor and time-point (T1/T4) will be the within-subjects factor. We hypothesize that there will be a significant interaction between group and time-point, with a larger improvement between pre- (T1) and post-scores (T4) in STEP-Home than PCGT. While we do not anticipate a significant interaction by cohort or site, we will evaluate the 4-way interaction and all 2-way and 3-way interactions for time-point, group, cohort, and site. The model will be rerun removing any non-significant interactions. Linear regression will be used to evaluate the difference in post-intervention (T4) by group. The final mixed and regression models for each outcome will adjust for any identified confounders.

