**Power Analysis.** Power calculations are made for the full study, including Phase 2 recruitment at site 2 (Houston). Power calculations were conducted on the primary aims (Aims 1 and 2) to observe an effect of Cohen's  $d=0.44$  or larger at one-tailed  $p<.05$  and  $\geq 80\%$  power. We selected a one-tailed p-value because all primary hypotheses were stated *a priori* as one-sided. We anticipated a small to medium effect size based on the Cohen's  $d=0.44$  observed in the subset of our SPiRE feasibility study ( $n=35$ ) who reported at least some difficulty on M2CQ, WHODAS, or Impulsive Aggression Scale (IAS). While we did not specifically collect pilot data on the PDRI or STAXI-2, we assume the effect size will be at least as strong as  $d=0.44$  observed on the proxy measures (WHODAS and IAS) since the PDRI and STAXI-2 are more sensitive and specific to post-9/11 Veterans. We further applied a conservative attrition rate of 20%, based on the attrition observed in our SPiRE feasibility study [1] and in Mt. Sinai's STEP RCT [2]. The univariate paired t-tests evaluating the improvement (Hypothesis 1A) and post-intervention maintenance (Hypothesis 2) of primary outcomes scores within the intervention groups required a total sample size of 83 after accounting for attrition. For Hypotheses 1B, the sample size was further adjusted to account for the clustering of subjects within the randomization cohort by applying an inflation of variance factor [71,89]. We used an interclass correlation of  $r=0.04$  as observed in a similarly designed group therapy RCT [65]. For the univariate post-intervention and change score analyses, we would need a total sample size of 208 after accounting for clustering and attrition. Thus, a total sample size of 208 is sufficient to power both primary aims.

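### The T4 between-arm regression (1B.2) names no cohort or therapy-group term, although its sample size allows for clustering at ICC 0.04; its one-sided 5% test runs between 4.7% and 6.7% at 6 analysed per group

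*Combined protocol and SAP*

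**What the plan says.** On the between-arm comparisons, the Power Analysis states that "the sample size was further adjusted to account for the clustering of subjects within the randomization cohort by applying an inflation of variance factor". The correlation used is 0.04, "as observed in a similarly designed group therapy RCT". It then concludes: "For the univariate post-intervention and change score analyses, we would need a total sample size of 208 after accounting for clustering and attrition". The T4 comparison is therefore one of the analyses that the plan itself treats as clustered.

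Under Aim 1, Hypothesis 1B, the plan gives two analyses for each primary outcome. Comparison 1B.1 is a PROC MIXED model of T1 and T4. The sentence on clustering within cohorts, the Satterthwaite option and the screening of cohort and site interactions all stand with that model. Comparison 1B.2 follows: "Linear regression will be used to evaluate the difference in post-intervention (T4) by group". The only further statement about it is that "The final mixed and regression models for each outcome will adjust for any identified confounders". Statistical Methods by Research Aims describes these as characteristics of subjects: "Any subject characteristics associated with both the treatment group and primary outcome measure will be adjusted for in the final statistical model". The clinical covariates listed under Baseline Comparability include neither cohort nor therapy group.

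Study Design says that each cohort is split into two equal therapy groups, one per arm, with 4 to 10 Veterans in each and a target of 8. It adds that "staff members will work in pairs when running groups". The comparator is described as a treatment that "emphasizes the process of interpersonal learning, group cohesion, and group support".

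**The concern.** The plan enrols extra participants because of clustering and then specifies a 1B.2 test whose standard error takes no account of it. Comparison 1B.2 is one of two between-arm tests on each of the three primary outcomes.

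Two kinds of correlation are possible, and they act in opposite directions. A cohort effect is shared by the STEP-Home group and the PCGT group of that cohort, so it cancels from the arm difference; ignoring it makes the plain regression slightly conservative. A therapy-group effect (leaders, group dynamics) belongs to one arm within one cohort and does not cancel; ignoring it makes the standard error too small, and benefit is declared too often. The plan's wording names the cohort. Its source for the ICC, its delivery format and its sample-size arithmetic point to the therapy group.

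**Working it through.** **Inputs.** From the Power Analysis: d = 0.44, one-sided 5%, 80% power, 20% attrition, ICC 0.04, N = 208. From Study Design: therapy groups of 8 (target) or 10 (maximum), equal arms within a cohort, 240 enrolled. From the extension note in the Analytic Plan: Cohort 20 is the last. Current average group size: 240 / 20 / 2 = 6.

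**Reproducing 208.** A one-sided two-sample t-test at d = 0.44 has 80.2% power with 65 per arm (79.7% with 64), so 130 in total.
- Therapy groups of 8: design effect 1 + 7 × 0.04 = 1.28, and 130 × 1.28 / 0.8 = 208.0.
- Whole cohorts of 16: design effect 1 + 15 × 0.04 = 1.60, and 130 × 1.60 / 0.8 = 260.0.

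The stated figure matches groups of 8. The plan does not show its working, so this is a reconstruction.

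**True error of the plain regression.** Set the total variance to 1. Let a share f of the ICC lie between therapy groups of size m and the rest between cohorts. The variance of the arm difference, relative to what plain regression assumes, is V = 1 − ICC + m × f × ICC. The true one-sided error is 1 − Φ(1.645/√V).

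| ICC 0.04 | m = 6 | m = 8 | m = 10 |
|---|---|---|---|
| All between therapy groups (f = 1) | V 1.20, 6.7% | V 1.28, 7.3% | V 1.36, 7.9% |
| Half (f = 0.5) | V 1.08, 5.7% | V 1.12, 6.0% | V 1.16, 6.3% |
| All shared cohort effect (f = 0) | V 0.96, 4.7% | V 0.96, 4.7% | V 0.96, 4.7% |

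V exceeds 1 when f > 1/m: 17% of the ICC at m = 6, 12.5% at m = 8, 10% at m = 10.

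The 0.04 is borrowed from another trial. Over an assumed ICC of 0.01 to 0.10 at m = 6, the error is 5.4% to 9.0% (f = 1), 5.2% to 6.7% (f = 0.5) and 4.9% to 4.2% (f = 0).

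**Simulation under the null** (100,000 replicates, ICC 0.04; f = 1 / 0.5 / 0).
- Plain regression: 6.6 / 5.6 / 4.7% with 20 cohorts and 6 per group; 7.5 / 5.9 / 4.7% with 13 cohorts and 8 per group.
- Within-cohort comparison of the two therapy groups: 4.9% to 5.1% in every case.
- With unequal group sizes: plain regression from 4.8% (f = 0) to 6.2% (f = 1); within-cohort comparison 4.8% to 5.1%.

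**Power of the within-cohort comparison** (noncentral t, cohorts minus 1 df, d = 0.44, one-sided 5%).

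| Design | f = 1 | f = 0.5 | f = 0 |
|---|---|---|---|
| 240 in 20 cohorts, 20% lost (4.8 per group) | 86% | 89% | 91% |
| 240 analysed in 20 cohorts (6 per group) | 91% | 94% | 96% |
| 208 in 13 cohorts, 20% lost (6.4 per group) | 78% | 82% | 86% |

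The first two rows reflect two readings of Study Design. It gives 240 as the enrolment total and says that 300 will be recruited to allow for dropout; 300 × 0.8 = 240, so 240 may already be net of dropout.

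**The case against.** The strongest objection is that both places where the plan names a clustering level say cohort. On that wording the error is 4.7% and nothing is inflated. This stands as far as it goes. A reader might infer from the omission that the 1B.2 test is shown to be anti-conservative; the documents do not support that. Every figure above 5% needs part of the ICC to lie between therapy groups, and the case for that is indirect: the group-therapy source of the ICC, groups led by staff pairs (the plan does not say whether one pair leads both arms), the emphasis on cohesion, and the reconstruction of 208.

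Second, the size is modest. The 7.3% figure needs 8 analysed per group, whereas 240 in 20 cohorts implies 6, hence 6.7% at most at ICC 0.04. That is right. Nor is 7.3% a ceiling, since groups of 10 are allowed.

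Third, a reader might infer that 1B.1 ignores clustering altogether. The plan does not support that either. It screens group-by-cohort and time-by-group-by-cohort interactions, which are the therapy-group terms, though it drops them if non-significant. It also cites a Section 6.2, absent from the supplied text, that may define more. The clustering sentence may even be meant to cover the regression; if so, the plan does not say it.

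Fourth, the remedy does not hold exactly 5% in every implementation. With variance components bounded at zero, simulated error is 3.7% to 4.6% with cohort fixed and 3.9% to 5.4% with cohort random. Multiple imputation was not simulated. These limits stand, and the fix below allows for the first.

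**Conclusion.** The concern holds as a mismatch between the sample-size calculation and the 1B.2 analysis. Clustering is allowed for in the first and not named in the second. At ICC 0.04 and 6 analysed per group, the one-sided 5% test runs between 4.7% (all shared cohort effect) and 6.7% (all between therapy groups). The upper end is 7.3% at the target of 8 and 7.9% at the maximum of 10. It passes 5% once more than 1/m of the ICC lies between therapy groups, and the documents do not settle that share.

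The figures assume randomization within cohort to two equal groups, as Study Design describes in detail (it also uses the term cluster randomization); one-sided testing, as in the Power Analysis; and no covariates, which could change the residual ICC.

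For 1B.1, Aim 2 and Exploratory Aim 1 there is only a point to confirm: the Satterthwaite option sets degrees of freedom and does not itself add a cluster variance.

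**What to change.** Analyse 1B.2 in PROC MIXED with arm, cohort (fixed or random) and a cohort-by-arm random effect for the therapy group, with Satterthwaite or Kenward-Roger degrees of freedom. Keep the therapy-group effect whatever its p-value, and state whether variance components may go below zero. In balanced data, cohort fixed with unbounded variances is the within-cohort comparison, which holds about 5% wherever the ICC lies. Name the therapy group as the clustering unit in the Hypothesis 1B methods and in the Power Analysis.

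For 1B.1 and the analyses that reuse it, confirm that Section 6.2 defines a retained therapy-group effect and a therapy-group-by-time effect, or state them. Supply or correct that reference.

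The cost is SAP wording and one or two model statements. Degrees of freedom fall to cohorts minus 1 (19 with 20 cohorts). At 6 per group, standard errors are about 10% larger if the ICC is all between therapy groups (√1.20 = 1.095), 4% larger if it is half (√1.08 = 1.039) and 2% smaller if it is all cohort (√0.96 = 0.980). With 240 in 20 cohorts, power stays above 80% on either reading of the enrolment figures, so no extra participants are needed. Only 208 in 13 cohorts with 20% lost falls below 80%, to 78%, and only if the ICC is all between therapy groups.

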### (b) Hypotheses & Aims

#### **Primary Aim 1. Examine treatment effects of STEP-Home on primary outcomes relative to Present Centered Group Therapy (PCGT):**

***Hypothesis 1A. Participants randomized into the STEP-Home intervention will show improvement on reintegration, readjustment, and anger post-intervention (expressed by lower scores; less difficulty).*** Military to Civilian Questionnaire (M2CQ), Post-Deployment Readjustment Inventory (PDRI), and State-Trait Anger Expression Inventory (STAXI-2) scores post-intervention (T4) < baseline (T1)

***Hypothesis 1B. Participants randomized into STEP-Home will show greater improvement in primary outcomes as compared to PCGT.***

Change scores baseline (T1) to post-intervention (T4) STEP-Home > PCGT change scores

Post-intervention (T4) primary outcome scores STEP-Home < PCGT primary outcome scores (T4)

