### Analytic Plan & Power Analysis

\* Analytic Plan & Power calculations may include references to the full study sample, including Phase 2 recruitment at site 2 (Houston).

\*\*The February 2023 project modification/1-year extension requested funds to complete Cohort 19 (ongoing at the time of the project modification request) and enroll one additional cohort (Cohort 20) to ensure sufficient power for Aim 1 (Hypotheses 1A, 1B) and Aim 2, and to support final data analysis and manuscript submission in the last 6 months of the 1-year cost extension (October 2023 – March 2024). Of note, the study's Aims, listed below, remain unchanged with the project modification. The only changes involve an increase in our targeted enrollment number, to ensure sufficient power, as enrollment and measures completion rates to date are slightly under our original goals.

Data Management. Data entered in the database will be verified and quality assurance procedures will be followed; Human Subjects (*Accuracy/ Integrity of Data*); Data management plan (“09\_VA\_DMAP”).

For continuous variables, the mean, median, standard deviation, minimum, maximum, interquartile range, and sample size for each intervention group will be reported at each time point. For categorical variables the frequency distribution will be reported for each treatment group.

Baseline Comparability. While no substantial differences between intervention groups are anticipated given randomization, we will use summary statistics, graphical techniques such as boxplots, and univariate analyses to compare baseline characteristics of groups. Pre-intervention values will be compared between

STEP-Home and PCGT groups using t-tests and chi-squared tests, as appropriate, to determine if the groups are balanced with respect to baseline characteristics. This comparison will allow us to identify potential confounders and moderators to be included in multivariate analyses. Clinical covariates include: age; education; diagnosis of TBI history; PTSD, mood disorder, anxiety, substance use, chronic pain, sleep quality.

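### Hypothesis 1B has two tests per outcome and no rule for which decides it; the T4 regression prespecifies neither the T1 score nor a clustering term

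*Combined protocol and SAP*

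**What the plan says.** In the Analytic Plan, Aim 1 divides Hypothesis 1B into 1B.1 (change from T1 to T4) and 1B.2 (score at T4), for each of M2CQ, PDRI and STAXI-2. For 1B.1 a mixed model tests the group-by-time interaction. For 1B.2: "Linear regression will be used to evaluate the difference in post-intervention (T4) by group". The text expects the interaction to be significant. It does not say whether 1B.1, 1B.2, either or both must succeed for 1B to be supported.

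On clustering, the mixed-model text says "The Satterwaite option will be used to account for the clustering of subjects within cohorts" and points to a Section 6.2. The regression sentence mentions no clustering. The Power Analysis paragraph nevertheless sizes both tests for it: "For the univariate post-intervention and change score analyses, we would need a total sample size of 208 after accounting for clustering and attrition".

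On covariates, "The final mixed and regression models for each outcome will adjust for any identified confounders". The rule for identifying them is "Any subject characteristics associated with both the treatment group and primary outcome measure will be adjusted for in the final statistical model". The screen is the set of baseline t-tests and chi-squared tests, of which the plan says "This comparison will allow us to identify potential confounders and moderators to be included in multivariate analyses". The named set reads "Clinical covariates include: age; education; diagnosis of TBI history; PTSD, mood disorder, anxiety, substance use, chronic pain, sleep quality". The T1 score of the outcome is not in it, although the assessment schedule collects all three measures at both T1 and T4.

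**The concern.** The two tests use the data differently and can fall on opposite sides of the significance threshold for the same outcome. With no rule for reading that result, what the trial claims on 1B would rest on a choice made after the data are seen.

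The T4 regression also leaves out the variable most likely to predict T4. Under the confounder rule, T1 enters only if it happens to be associated with treatment group. Randomisation makes that uncommon, however strongly T1 predicts T4. The model for a primary hypothesis would then be chosen by the data, and the precision that T1 offers would usually go unused.

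Finally, the T4 regression as described does not match the basis on which it was sized.

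**Working it through.** **Inputs.** From Power Analysis: d=0.44, one-sided 5%, at least 80% power, ICC 0.04, attrition 20%, N=208. From Study Design: 1:1 allocation, goal of two therapy groups of 8 per cohort, enrolment target 240. Assumed, because the documents do not give them: T1–T4 correlation ρ of 0.3 to 0.7, d scaled on the T4 SD, equal T1 and T4 SDs.

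**1. The plan's figure.** A two-sample t-test needs 65 per arm (80.2% power). The design effect is 1 + (8 − 1) × 0.04 = 1.28. Then 65 × 2 × 1.28 / 0.8 = 208. The match is exact with the therapy group of 8 as the cluster; a cluster of 16 would give 260.

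**2. Variances.** With n analysed per arm (208 × 0.8 / 2 = 83.2), and in units of the T4 variance, n times the variance of an arm mean is as follows.
- Case A, where using T1 also reduces the group component: T4-only 1.28; change 1.28 × 2(1 − ρ); T1-adjusted 1.28 × (1 − ρ²).
- Case B, where the group component arises only after T1 (plausible, since groups form after baseline): 1.28; 2(1 − ρ) + 0.28; (1 − ρ²) + 0.28.

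The noncentrality is 0.44 / √(2v/n). Example at ρ=0.5, case A: T4-only 0.44 / √(2.56/83.2) = 2.51; T1-adjusted 0.44 / √(1.92/83.2) = 2.90.

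**3. Agreement of the two planned tests.** Their statistics are treated as bivariate normal, with correlation √((1 − ρ)/2) in case A and (1 − ρ + 0.28) / √(1.28 × (2(1 − ρ) + 0.28)) in case B. The chance that they split is P1 + P2 − 2·P(both). At ρ=0.5, case A: 0.806 + 0.806 − 2 × 0.696 = 0.22.

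Results at N=208, in %, with the range over cases A and B:

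| ρ | Power, T4-only | Power, change | Power, T1-adjusted | Tests split | Power if both required |
|---|---|---|---|---|---|
| 0.3 | 80.3 | 68.0–70.4 | 82.8–83.5 | 22.0–25.4 | 61.7–64.7 |
| 0.5 | 80.3 | 80.3 | 87.3–89.2 | 19.5–22.1 | 69.6–70.8 |
| 0.6 | 80.3 | 85.9–87.5 | 90.3–93.0 | 18.7–20.7 | 73.8–74.0 |
| 0.7 | 80.3 | 91.4–94.3 | 93.8–96.8 | 18.3–19.8 | 77.0–77.6 |

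At 240 less 20% (n=96 per arm), T4-only power is 85% and the tests split in 14–22% of trials.

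**4. Sensitivity to the scaling of d and the T1 SD (N=208).** If d is on the change-score SD, T4-only power at ρ = 0.3/0.5/0.6/0.7 is 90/80/72/61%, change 80–82/80/78–80/75–80%, and T1-adjusted 92–93/87–89/84–87/79–86%. If the T1 SD is 0.8 of the T4 SD, the variance gap between change and T1-adjusted is (0.8 − ρ)², so the gain over change nearly vanishes at ρ=0.7.

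**5. If the T4 regression ignored clustering.** With the therapy group as the cluster, the actual one-sided error is P(Z > 1.645/√DE), with DE = 1 + (m − 1) × 0.04.
- Groups of 8 less 20%: m = 6.4, DE = 1.216, error 6.8%.
- If cohorts are numbered consecutively up to Cohort 20, 240 enrolled in 40 groups gives 6 each: m = 6 × 0.8 = 4.8, DE = 1.152, error 6.3%.
- T1 added without a clustering term, case B: the residual ICC is 0.04/(1 − ρ²). At ρ=0.7 this is 0.078, DE = 1 + 5.4 × 0.078 = 1.42, error 8.4% at m = 6.4 (7.0% at ρ=0.3). In case A it stays at 6.8%.

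If instead the effect is shared by a whole cohort, it cancels in the arm contrast, because each cohort supplies equal numbers to both arms. A simulation with 13 cohorts, 8 per arm and a cohort-level ICC of 0.04 gave 4.5% with clustering ignored.

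**The case against.** The strongest defence is that the plan already leans one way. Hypothesis 1B speaks of greater improvement, the interaction is the only result the text expects to be significant, and 1B.1 and 1B.2 are separately labelled, so a split could simply be reported as a split. That is a fair reading. But an expectation is not a decision rule, and Power Analysis sizes the two tests alike without ranking them.

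A reader might infer that success on either test would be accepted, which would put the one-sided error per outcome at about 8.2–9.1%. Nothing in the document states or implies that rule, so this inflation cannot be charged to the plan.

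It can also be said that the mixed model already uses T1, that a marked T1 imbalance would trigger adjustment, and that the rest is a preference about efficiency. Much of this stands: the gain depends on a correlation and a scaling that the documents do not give, and it is about 3 points over T4-only at ρ=0.3. The objection does not remove the data-driven route by which T1 would enter.

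On clustering, the plan's word is cohort, and a cohort contains both arms. Section 6.2, to which the plan refers, is not in the supplied text and may define the term. Both points stand. A reader might infer a firm error of 7.3%, or up to 9.3% with T1 added; those figures need 8 analysed per group with no loss, which contradicts the plan's own 20% attrition.

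**Conclusion.** The point holds as a missing decision rule plus avoidable loss of precision. It is not a finding of bias or of a wrong sample size: both planned estimates are unbiased under randomisation, and 208 reproduces.

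Under the stated assumptions the two planned tests would disagree in about 18–25% of trials at N=208. Requiring both would leave 62–78% power, below the planned 80%. One T1-adjusted model would give 83–97%, against 80% for T4-only and 68–94% for change. In large samples its variance is no greater than that of either planned test.

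The clustering limb is conditional and carries moderate confidence. If the cluster is the therapy group (the reading under which 208 reproduces) and the T4 regression ignored it, one-sided error would be roughly 6–7% at about 5 to 6.4 completers per group, and up to about 8.4% if T1 were added without a clustering term. If the effect is shared across a cohort, there is no inflation. The wording gaps themselves do not depend on any assumed number. This should be settled before outcome data are analysed.

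**What to change.** For each primary outcome, name one governing test of Hypothesis 1B: the T4 score on group, with the T1 score of the same measure as covariate, in a mixed model with a random effect for therapy group within cohort. A T1/T4 mixed model with a common T1 mean across arms and the same random effect is equivalent. State the random effect explicitly, because Satterthwaite is a method for degrees of freedom and does not itself model clustering. Label the other 1B analysis supportive and say that it does not decide 1B. Use the baseline t-tests and chi-squared tests for description only, not to select covariates.

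The cost is SAP wording and one degree of freedom for T1, which is already collected. Testing on group-level degrees of freedom (26 − 2 = 24 with 26 groups of 8, or 40 − 2 = 38 if 20 cohorts are run) also has a price: at 24, about 1–2 points of power, much the same for all three analyses. No extra participants are needed. This does not deal with multiplicity across the three primary outcomes, which needs its own rule.
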